8.2. Cumulative Dose and Dose Intensity

The cumulative actual dose and actual dose intensity for each study drug (CC-122, ibrutinib, obinutuzumab) will be presented by dose cohort for each arm. The actual dose intensity is defined as the cumulative actual dose divided by the total length of treatment for the IP.

CC-122:

The cumulative actual dose of CC-122 is defined as the sum of all doses of CC-122 taken across the treatment period.

The cumulative expected dose of CC-122 is calculated as below:

- For the cycles on daily schedule of CC-122 (only applicable to Arm A subjects):

Expected dose = (stop date - start date of CC-122 administration +1) \times planned daily dose;

- For the cycles on 5/7 days schedule of CC-122:

$$\text{Expected dose} = \text{Planned daily dose} \times \left[\left\lfloor \frac{\text{Dur}}{7} \right\rfloor \times 5 + \min \left(5, \text{Dur} - \left\lfloor \frac{\text{Dur}}{7} \right\rfloor \times 7 \right) \right], \text{ where}$$

Dur is the treatment duration for CC-122.

Repeat this derivation for each planned dose (i.e. take into account the dose escalation but not the decrease due to AE) and sum up.

The Expected dose intensity for CC-122 is the cumulative expected dose divided by the total length of treatment duration for CC-122.

Ibrutinib (Arm B)

The cumulative actual dose of ibrutinib is the sum of all doses of Ibrutinib taken across the treatment period. The cumulative expected dose of ibrutinib is the (planned daily dose \times Ibrutinib treatment duration in days). The expected dose intensity for Ibrutinib is the planned daily dose – 420 mg/day.

Obinutuzumab (Arm C):

The cumulative actual dose of obinutuzumab is the sum of all doses of obinutuzumab taken across the treatment period. The cumulative expected dose of obinutuzumab is the sum of the planned dose per Table 10 in the protocol Section 8.2.2.3 based on the last visit which has been completed:

Last visit completed	Cycle 1 Day 1	Cycle 1 Day 2	Cycle 1 Day 8	Cycle 1 Day 15	Cycle 2 Day 1	Cycle 3 Day 1	Cycle 4 Day 1	Cycle 5 Day 1	Cycle 6 Day 1
Cumulative expected dose (mg)	100	1000	2000	3000	4000	5000	6000	7000	8000

The Expected dose intensity for obinutuzumab is the cumulative expected dose divided by the total length of treatment duration for obinutuzumab.

8.3. Relative Dose Intensity

Relative dose intensity is used in place of the treatment compliance. Relative dose intensity is defined as actual dose intensity divided by expected dose intensity.

Additionally, the number and percentage of subjects will be summarized by $\leq 80\%$ and $>80\%$ for relative total dose intensity of CC-122, for CC-122 and ibrutinib in Arm B, for CC-122 and obinutuzumab in Arm C, the actual category can be data driven.

8.4. Dose Reduction/Interruptions

Dose reduction is defined as a decrease in dose (non-zero) relative to the immediately previous dose (or assigned dose if the first dose). Dose interruption occurs if the record of actual administered dose is zero except as required by the protocol (i.e. for CC-122 the 2 out of 7 days when the subject does not receive CC-122 drug). If an interruption happens at the start of a cycle and causes the cycle to be postponed, it is also called dose delay. Consecutive zeros are counted as one interruption. The reductions will be derived from the data collected.

Dose modifications are permitted in any cycle, including Cycle 1 and the DLT evaluation period:

- Dose reductions that occur during the DLT evaluation period will constitute a DLT, but subjects will be allowed to continue on IP at a reduced dose.

- Dose reductions are allowed for CC-122 and ibrutinib. No dose reductions are allowed for obinutuzumab, but treatment may be discontinued at the discretion of the investigator for severe infusion or allergic reactions.

Dose reduction, where applicable, and interruption will be summarized separately by dose cohort and overall for each arm. Summaries include the following:

- Number of subjects with dose reductions or interruptions;
- Number of dose reductions/interruptions due to AE;
- Descriptive statistics of time to the first dose reduction or interruption (from the first dose) due to an AE for those who have at least one dose reduction or interruption due to an AE;
- Descriptive statistics of total days of dose reduction or interruption due to an AE for those who have at least one dose reduction or interruption of CC-122 and Ibrutinib due to an AE;
- Number and percentage of subjects who have at least two dose reductions or interruptions.

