8.2.9.2. Dose Modification Guidelines

Any IP-related toxicity meeting the definition of DLT will require dose reduction or interruption. The criteria for dose reduction are listed in [Table 14](#), should be used for dose modifications.

Chronic Grade 2 toxicity (other than specified below) may warrant dose reduction or interruption of one or both IP. Such cases should be discussed with the sponsor's medical monitor before changes are made.

Dose modification decisions for patients with cytopenia (below the lower limit of the normal range) at **baseline** will be based on the IWCLL guideline ([Table 13](#)). For patients with a normal neutrophil count, platelet count and/or hemoglobin value at baseline, the NCI CTCAE (version 4.03) will be used.

Any dose modifications must be recorded on the respective Study Drug Record eCRF.

Table 14: Dose Reduction Guidelines

Adverse Event	Grade	Action	Agent to be considered for interruption/reduction (in descending order)
Thrombocytopenia	≥ Grade 3	
• Hold all IP• Follow CBC at least every 7 days• If thrombocytopenia resolves to ≤ Grade 2, restart IP and reduce CC-122 to the next lower dose level. Ibrutinib may be restarted after thrombocytopenia resolves to ≤ Grade 1 or baseline at original dose after the 1st occurrence, and reduce by one dose level at each subsequent recurrence with a maximum of 2 dose reductions allowed. A 4th recurrence requires permanent discontinuation of ibrutinib.• Obinutuzumab should be restarted at the full dose after thrombocytopenia resolves to ≤ Grade 2, no dose reduction is allowed.	
• CC-122• Ibrutinib/obinutuzumab

Table 14: Dose Reduction Guidelines (Continued)

Adverse Event	Grade	Action	Agent to be considered for interruption/reduction (in descending order)

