8.2.12.2. Ibrutinib Dose Reduction Steps

Ibrutinib dose reduction steps are shown in [Table 16](#).

Table 16: Ibrutinib Dose Reduction Steps

Non-Hematologic Adverse Events	
Toxicity Occurrence	Action to be Taken
First	Withhold ibrutinib until recovery to Grade \leq 1 or baseline; may restart at original dose level, 420 mg daily
Second	Withhold ibrutinib until recovery to Grade \leq 1 or baseline; may restart at 1 dose level lower, 280 mg daily
Third	Withhold ibrutinib until recovery to Grade \leq 1 or baseline; may restart at 1 dose level lower, 140 mg daily
Fourth	Discontinue Ibrutinib

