 - First dose date of IP corresponds to the earliest date any dose (of CC-122, ibrutinib, or obinutuzumab) has been initiated (i.e. a non-zero dose was administered/infused).
 - Last dose date of IP corresponds to the latest date any dose (of CC-122, ibrutinib, or obinutuzumab) has been administered/infused.
- 

Time points beyond Cycle 12 will not be displayed in the by cycle summary due to limited sample size and the allowed flexible frequency of the test/measurement. Data from all time points will be included to evaluate the “most extreme” post-baseline value.

- For subjects in Arm A who have disease progress (PD) and then are treated with Ibrutinib or Obinutuzumab, following conversions will be applied:

- In the database, the cycles after PD/arm switch will be labeled with suffix “-PD” and started from “Cycle 1 Day 1”. For summary and reporting purpose, those visits will be mapped to the cycle numbers based on their original treatment schedule. For example, if a subject switch to Arm B (CC-122 plus Ibrutinib) after Cycle 2, the next visit labeled as “Cycle 1 Day 1 - PD” will be mapped as “Cycle 3 Day 1” and summarized accordingly.
 - Efficacy data collected up to the PD/arm switch, and all safety data collected in the study will be included in the summary under Arm A (and the starting dose level of CC-122 they initially received).
 - For study treatment and exposure summaries, the data collected before the treatment switch will be summarized under “CC-122 xx mg” according to the subject’s initial CC-122 dose, the data collected after the treatment switch will be summarized under “CC-122 + Ibrutinib”, or “CC-122 + Obinutuzumab”, according to which drug the subject received.
 - Subjects who switch the treatment can report AEs which are
 - related to Ibrutinib or Obinutuzumab,
 - leading to discontinuation/reduction/interruption of Ibrutinib or Obinutuzumab.

Those TEAEs will be summarized under Arm A (and starting dose of CC-122 they initially received).

- For subjects in Arm C who are not treated with CC-122:

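### SAP 8.4 compares each dose with the record just before it, which is zero after a hold, so a hold followed by a lower restart is not counted as a dose reduction

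*SAP*

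**What the plan says.** SAP 8.4 gives the reduction rule: "Dose reduction is defined as a decrease in dose (non-zero) relative to the immediately previous dose (or assigned dose if the first dose". It then defines the other event: "Dose interruption occurs if the record of actual administered dose is zero except as required by the protocol". The protocol-required zeros it has in mind are the two days off in each seven-day CC-122 week. On runs of zeros it says "Consecutive zeros are counted as one interruption", and on the source of the count it says "The reductions will be derived from the data collected". Reductions and interruptions are to be summarised separately. The summaries cover subjects affected, events due to an adverse event, time to the first event, total days, and subjects with at least two.

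The protocol describes how reductions come about. Section 8.2.9.1 makes interruption the default for related events of Grade 3 or higher, unless Table 14 directs otherwise. In the thrombocytopenia row of Table 14 all drugs are held first. On recovery the instruction is to "restart IP and reduce CC-122 to the next lower dose level". In Table 16, the second ibrutinib occurrence is a withhold, after which the subject "may restart at 1 dose level lower, 280 mg daily". The third occurrence follows the same pattern, down to 140 mg.

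**The concern.** The comparator is the record just before the current one. After a hold that record is zero, and no restart dose can be lower than zero. The hold is therefore counted as an interruption, and the lower restart is not counted as anything. Hold-then-restart-lower is the protocol's main route to a reduced dose, so the rule fails in the ordinary case.

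What is at stake is the set of reduction summaries in SAP 8.4, which describe tolerability in a trial whose primary objectives are safety and tolerability. Two programmers working from the same text could also report different counts from the same records.

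**Working it through.** The plan gives no figure to reproduce, so the check applies the rule to dose sequences.

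**Inputs.** The rule and the zero-dose convention come from SAP 8.4. CC-122 levels come from protocol Table 15 (from 2.0 mg, the first two steps are 1.5 and 1.0 mg). Ibrutinib levels come from Table 16 (420, 280, 140 mg). The sequences are illustrative, not trial data.

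**Formulas.** Let d(i) be the dose in record i, with the assigned dose as comparator for the first record.

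- As written: count record i if d(i) > 0 and d(i) < d(i−1).
- Alternative: count record i if d(i) > 0 and d(i) is below the last non-zero dose before it.

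| Sequence (mg) | As written | Last non-zero comparator |
|---|---|---|
| CC-122 2.0, 0, 1.5 | 0 | 1 |
| CC-122 2.0, 0, 1.5, 0, 1.0 | 0 | 2 |
| CC-122 2.0, 0, 2.0 | 0 | 0 |
| CC-122 2.0, 1.5 (no hold) | 1 | 1 |
| Ibrutinib 420, 0, 420, 0, 280, 0, 140 | 0 | 2 |

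In the first line, 2.0 to 0 is an interruption, and 1.5 is then compared with 0, which is an increase. The alternative rule finds the true reductions and adds none when the subject restarts at the same dose.

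**Scheduled days off.** SAP 8.4 exempts these zeros only from the definition of an interruption. Suppose they are stored as zero records. Five days at 2.0, two at 0, then five at 1.5 gives 0 as written and 1 with the alternative, with no hold at all. A midweek change (two days at 2.0, three at 1.5, two at 0, five at 1.5) gives 1 under both. The documents do not show how these days are stored.

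**How much of Table 14 is exposed.** Rows in which CC-122 can be lowered:

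- Hold directed (5): thrombocytopenia, neutropenia, troponin-T/BNP, TLS Grade 2-4, creatinine clearance below 30 mL/min. The neutropenia and troponin-T/BNP rows also allow a restart at the same dose.
- Hold at the investigator's discretion (5): AST/ALT/bilirubin, diarrhea, peripheral neuropathy, the row for other events, pneumonitis Grade 2.
- No hold (2): laboratory or Grade 1 TLS, creatinine clearance 30-49 mL/min.

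That is 5 + 5 = 10 rows with a hold, out of 10 + 2 = 12. For ibrutinib, both lower steps in Table 16 follow a withhold (2 of 2).

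**Effect on each 8.4 summary.** Counts of subjects with reductions, of AE-related reductions and of subjects with at least two can only fall. Time to first reduction and total days are described only among subjects who have an event. A missed early reduction either drops the subject or is replaced by a later one, so the direction of the error is indeterminate.

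**The case against.** **The wording allows another reading.** The parenthesis in the rule could be taken to describe the comparator, and SAP 5.1 shows that the SAP thinks of a dose as drug actually given ("i.e. a non-zero dose was administered/infused"). This is strained. The parenthesis follows the decrease and separates a reduction from an interruption. SAP 5.1 shows instead that the SAP spells out non-zero where zeros are to be ignored. It is fair, however, that programming specifications and the layout of the dosing form are not visible, so an actual undercount cannot be shown.

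**Tolerability is reported elsewhere.** This stands in part. SAP 11.1.1 tabulates treatment-emergent adverse events that led to a reduction, including those with onset in CC-122 cycles 2 to 6. Relative dose intensity (SAP 8.2 and 8.3) also reflects the lost dose, because the expected dose is not lowered for decreases due to adverse events. These outputs limit the harm. They do not correct the 8.4 table, and they could disagree with it.

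**Only two Table 14 rows could register a reduction.** A reader might infer this from the row count, but it does not follow. In five rows the hold is discretionary. Protocol 8.2.9.2 also lets chronic Grade 2 toxicity lead to a reduction without a hold, and the atrial fibrillation row mentions a lower ibrutinib dose with no withhold stated. Reductions made by these routes are counted. Rows are also not events.

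**The primary endpoint is affected.** A reader might infer this because SAP 8.4 also says "Dose reductions that occur during the DLT evaluation period will constitute a DLT". The documents do not support it. SAP 11.1.2 identifies DLTs as treatment-related adverse events that meet protocol 8.2.7, and that section already covers events necessitating a lower dose level in the window. Nothing instructs anyone to flag DLTs from consecutive dose records.

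**Conclusion.** The defect stands. As written, SAP 8.4 counts a hold with a lower restart as an interruption only. It misses both Table 16 ibrutinib reductions and every CC-122 reduction made after a hold. The three reduction counts in 8.4 would be too low, and the time and duration summaries would be unreliable in either direction.

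This assumes that holds are stored as zero records and that the programmer follows the text. The share of actual reductions missed is unknown, because the documents contain no dosing data. The effect is confined to descriptive exposure summaries and to their agreement with SAP 11.1.1. The documents do not support a conclusion that DLTs would be miscounted, or that tolerability as a whole would be misreported.

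**What to change.** Replace the definition in SAP 8.4 as follows. A dose reduction is a non-zero dose lower than the last preceding non-zero dose of the same drug, or lower than the assigned dose if it is the first dose. Zero records from holds and from scheduled days off are ignored when the comparator is chosen. A hold followed by a lower restart counts as one interruption and one reduction.

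The cost is one sentence in the SAP and one line of derivation code, to be settled before database lock. After the change, compare the 8.4 reductions due to adverse events with the SAP 11.1.1 tables and resolve any difference. No clinical rule in the protocol needs to change.

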9. PRIOR/CONCOMITANT MEDICATIONS AND PROCEDURES

Medications initiated prior to the start of first dose of IP (i.e. any study drug) and are continued after the first dose of IP will be counted as both prior and concomitant medications.

Summary tables of prior and concomitant medications and prior and concomitant procedures will be provided for the Safety population. Listings will also be provided for all enrolled subjects.

The Anatomical Therapeutic Chemical (ATC) coding scheme of the World Health Organization (WHO) Drug Dictionary (WHODrug) will be used to group medications into relevant categories for these tabulations. Individual listings of prior and concomitant medications/procedures will be provided to support the tables.

9.1. Prior Medications

Prior medications are defined as medications that were started before the first dose of the study drug and either ended before the start of the study treatment or continued after initiation of study treatment. Prior medications will be summarized in frequency tabulations by dose cohort and overall for each treatment arm and by ATC level 2 category and preferred drug name.

9.2. Concomitant Medications

Concomitant medications are defined as non-study medications that were either initiated before first dose of any study drug and continued during the study treatment or initiated during the study treatment exposure period, defined as the interval between the date of first administration of any study treatment and the last dose of any study treatment plus 28 days. Concomitant medications will be summarized in frequency tabulations by treatment arm, dose cohort and overall and by ATC level 2 category and preferred drug name.

In addition, the number of subjects with concomitant growth factor will be summarized in frequency tabulations by treatment arm, dose cohort and overall and by ATC level 2 category and preferred drug name.

9.3. Concomitant Procedures and Surgeries

Concomitant procedures/surgeries will be summarized by SOC and PT coded with the MedDRA dictionary Version 22.0 or higher using frequency tabulations by treatment arm, dose cohort and overall. Concomitant procedures/surgeries are defined as procedures/surgeries that were performed during the study treatment exposure period, defined as the interval between the date of first administration of any study treatment and the last dose of any study treatment plus 28 days. Concomitant procedures/surgeries will be listed.

[REDACTED]

[REDACTED]

[REDACTED]

10. EFFICACY ANALYSIS

The efficacy endpoints of this study include ORR, MRD, DoR and PFS based on the International Workshop on Chronic Lymphocytic Leukemia (IWCLL) [REDACTED] with modifications [REDACTED] [REDACTED] for subjects with CLL and based on the revised International Workshop Lymphoma criteria for response assessment [REDACTED] for subjects with SLL. For subjects with CLL see [Table 3](#) for details and for subjects with SLL see [Table 4](#) for details. Lymph node responses will be assessed separately and independently of increases in blood lymphocyte counts.

Efficacy response according to the respective criteria for CLL/SLL will be formally assessed every three cycles during the first two years and every 6 cycles thereafter at the time of physical examinations until documented progression or initiation of subsequent CLL therapy. PD based on physical and/or laboratory tests at any time should be confirmed by CT scan. CR/CRI confirmation by bone marrow examination must be completed within 12 weeks after clinical criteria have been met. Furthermore, CT scans at Screening, end of Cycle 6 are mandatory (the 2nd scan is mandatory only for the affected regions with abnormal findings at baseline; Week 25 (for subjects on Arms A and C) or Week 29 (for subjects on Arm B), +4 weeks/-1 week).

Tables and listings will be provided to describe the efficacy endpoints tabulated by dose cohort and overall for each treatment arm. Efficacy analysis will include a summary of ORR, MRD, DoR and PFS.

For each subject the survival status will be provided in a listing.

In addition, a waterfall of the best percentage change from baseline sum of the product of the perpendicular diameters for multiple lesions will be provided for subjects with measurable nodal lesions at baseline. Each subject's best percent change will be represented by a bar, with a pattern specific to the dose level to which they were initially assigned to (in dose escalation phase).

10.1. Objective Response Rate (ORR) and Minimal Residual Disease (MRD)

For subjects treated with CC-122 and CC-122 in combination with ibrutinib or obinutuzumab, investigators will use the updated IWCLL guidelines for diagnosis and treatment of CLL [REDACTED] with modifications [REDACTED] for subjects with CLL and the revised International Workshop Lymphoma criteria for response assessment [REDACTED] for subjects with SLL.

Table 3: Response Definition after Treatment for Chronic Lymphocytic Leukemia Subjects

	Parameter	Complete Response*	Partial Response*	Partial Response with Lymphocytosis*	Progressive Disease***
Group A	Lymphadenopathy	None > 1.5 cm	Decrease \geq 50% from the baseline in the SPD of the index nodal lesions	Decrease \geq 50% from the baseline in the SPD of the index nodal lesions	Increase from the nadir by \geq 50% in the SPD of lesions or new lesion**
	Hepatomegaly	None	Decrease in the enlargement of the liver by \geq 50% (minimum 2 cm decrease) from baseline or LVD decrease to \leq 18 cm by imaging	Decrease in the enlargement of the liver by \geq 50% (minimum 2 cm decrease) from baseline or LVD decrease to \leq 18 cm by imaging	Increase \geq 50% in the enlargement of the liver from nadir (with a minimum 2 cm increase and a minimum LVD of 20 cm) or new lesion**
	Splenomegaly	None	Decrease in the enlargement of spleen by \geq 50% (minimum 2 cm decrease) from baseline or LVD decrease to \leq 12 cm by imaging.	Decrease in the enlargement of spleen by \geq 50% (minimum 2 cm decrease) from baseline, or LVD decrease to \leq 12 cm by imaging.	Increase \geq 50% in splenic enlargement from nadir (with a minimum 2 cm increase and a minimum LVD of 14 cm) or new lesion**
	Blood Lymphocytes	< 4000/ μ L	Decrease \geq 50% from baseline	Persistent lymphocytosis due to mechanism of action of IP	Increase \geq 50% over nadir (with at least ALC of 5000/ μ L)
	Marrow	Normocellular, < 30% lymphocytes, no B-lymphoid nodules Hypocellular marrow defines Cri	50% reduction in marrow infiltrate, or B-lymphoid nodules	50% reduction in marrow infiltrate, or B-lymphoid nodules	-

Table 3: Response Definition after Treatment for Chronic Lymphocytic Leukemia Subjects (Continued)

	Parameter	Complete Response*	Partial Response*	Partial Response with Lymphocytosis*	Progressive Disease***
Group B	Platelet count	> 100,000/ μ L	> 100,000/ μ L or increase $\geq 50\%$ over baseline	> 100,000/ μ L or increase $\geq 50\%$ over baseline	Current platelet is < 100 x $10^9/L$ and there has been a decrease of $\geq 50\%$ from baseline secondary to CLL
	Hemoglobin	> 11.0 g/dL	> 11.0 g/dL or increase $\geq 50\%$ over baseline	> 11.0 g/dL or increase $\geq 50\%$ over baseline	The current hemoglobin is < 11 g/dL and there has been a decrease of > 2g/dL from baseline secondary to CLL
	Neutrophils	> 1500/ μ L	> 1,500/ μ L or increase $\geq 50\%$ over baseline	> 1,500/ μ L or increase $\geq 50\%$ over baseline	-

Abbreviations: ALC = absolute lymphocyte count; CLL = chronic lymphocytic leukemia; CRi = complete response with incomplete marrow recovery; IP = investigational product; LD = longest diameter; LPD = longest perpendicular diameter; LVD = longest vertical dimension; SPD = sum of the product of the perpendicular diameters for multiple lesions.

Notes:

* Complete Response (CR): all of the criteria have to be met, and subjects have to lack disease-related constitutional symptoms; Partial Response (PR) and Partial Response with Lymphocytosis (PRL): at least two of the criteria of Group A plus one of the criteria of Group B have to be met. There are two exceptions in which only 1 criterion is needed: 1) only lymphadenopathy is present at baseline (applicable to PR only); 2) only lymphadenopathy and lymphocytosis are present at baseline. In these two scenarios (applicable to PRL only), only lymphadenopathy must improve to the extent outlined in the Group A criteria in the table; Stable Disease (SD) is the absence of Progressive Disease (PD) and failure to achieve at least PR; PD: at least one of the above criteria of Group A or Group B has to be met. Lymphocytosis as a criterion for PD is not applicable to ibrutinib treated subjects and generally requires other supportive evidence of PD. Response or PD assessment of lymphadenopathy may also be based on longest diameters of the enlarged lymph nodes and the same method should be applied consistently to all lesions.

**New lesion is defined as any of the following: a new node that measures >1.5cm in the LD and >1.0 cm in the LPD; new or recurrent hepatomegaly ≥ 20 cm in LVD; new or recurrent splenomegaly ≥ 14 cm in LVD; unequivocal appearance or re-appearance of an extra-nodal lesion of any size; New non-index disease (ascites, pleural effusion, or other abnormalities) confirmed to be related to CLL progression.

***Additional criteria for PD include: 1) transformation to a more aggressive histology (e.g., Richter syndrome) as established by biopsy (the date of biopsy being the date of progression in the subject who has no earlier objectively documented CLL progression). 2) Unequivocal increase in size of non-index disease (e.g., effusions, ascites, or other organ abnormalities confirmed to be related to CLL).

Table 4: Summary of Revised Criteria for Response Assessment for Small Lymphocytic Lymphoma

Response Category	PET-CT-Based Response	CT-Based Response
CR	Complete metabolic response Score 1, 2, or 3 with or without a residual mass on 5PS A complete metabolic response even with a persistent mass is considered a complete remission	Target nodes/nodal masses must regress to ≤ 1.5 cm in longest diameter No extralymphatic sites of disease
PR	Partial metabolic response Score 4 or 5 with reduced uptake compared with baseline and residual masses of any size	All of the following: $\geq 50\%$ decrease in SPD of up to 6 target measurable nodes and extranodal sites Spleen must have regressed by $> 50\%$ in length beyond normal
SD	No metabolic response Score 4 or 5 with no significant change in FDG uptake from baseline	$< 50\%$ decrease from baseline in SPD of up to 6 dominant, measurable nodes and extranodal sites No criteria for PD are met
PD	Progressive metabolic disease Score 4 or 5 with an increase in intensity of uptake from baseline and/or New FDG-avid foci consistent with lymphoma Bone marrow: New or recurrent FDG-avid foci	At least 1 of the following: An individual node/lesion must be abnormal with: Longest diameter > 1.5 cm and increase by $\geq 50\%$ from nadir and An increase by longest diameter or shortest diameter from nadir In the setting of splenomegaly, the splenic length must increase by $> 50\%$ of the extent of its prior increase beyond baseline New or recurrent splenomegaly New or clear progression of pre-existing non-measured lesions Regrowth of previously resolved lesions Bone marrow: New or recurrent involvement

Abbreviations: 5PS: 5-point scale; CR=complete response; CT = computed tomography; FDG = fluorodeoxyglucose; PET = positron emission tomography; PR = partial response; PD = progressive disease; SPD = sum of the product of the perpendicular diameters for multiple lesions.

Definition: nadir = the smallest value from all previous lesion size assessments (not including the current assessment).

Peripheral blood for MRD assessment will be collected during screening, every 6 cycles (only if subjects are receiving CC-122, up to a maximum of 24 cycles), and at the time of Complete Response (CR) and/or Complete Response with incomplete marrow recovery (CRi) confirmation visit (within 12 weeks after clinical and laboratory response criteria have been met). For those subjects confirmed to be MRD positive in the peripheral blood at the CR/CRi confirmation visit, a peripheral blood sample for MRD assessment will be collected approximately every 6 cycles thereafter until MRD negativity is achieved or relapse/progression is documented.

Peripheral blood for MRD assessment will also be collected at the time of Partial Response (PR), including Partial Response with Lymphocytosis (PRL), within 12 weeks after clinical, imaging, and laboratory

response criteria have been met. Peripheral blood for MRD assessment should also be collected at the time of relapse/progression in subjects who previously achieved MRD negativity in peripheral blood. MRD analyses will be performed by a central laboratory.

Response will be assessed by the investigator using modified IWCLL guidelines for diagnosis and treatment of CLL for CLL subjects and the revised International Workshop Lymphoma criteria for response assessment for SLL subjects. The response rate based on the best response during the treatment period and the relative proportions in each response category will be examined. Distributions of the responses into the response categories (CR, CRi, nodular Partial Response [nPRL], PR, PRL, stable disease [SD], PD with histologic transformation [PDwH] and PD without histologic transformation [PDw/oH], not evaluable, not evaluable due to TFR and other) will be provided for each treatment arm and dose level.

ORR will be the proportion of subjects with (CR + CRi + PR + nPR + PRL [PRL is only applicable to Arm B]). ORR will be summarized by dose cohort and overall for each treatment arm for the Safety and the EE populations. The corresponding two-sided 95% CI will be calculated for CLL/SLL cohorts using Clopper-Pearson [REDACTED] method.

Response rate will also be presented for end of cycle 3, end of cycle 6 and end of cycle 12 assessments. As the length of cycles can be varied due to dose escalation, following rules will be applied to the summary:

- for the best response at the end of cycle 3, responses collected up to Day 85 will be used;
- for the best response at the end of cycle 6, responses collected up to Day 169 will be used; only subjects who have assessment beyond Cycle 3 (Day 85) are included in this summary;
- for the best response at the end of cycle 12, responses collected up to Day 337 will be used; only subjects who have assessment beyond Cycle 6 (Day 169) are included in this summary.

MRD negativity rate will be presented using frequency counts and percentages together with CIs for each treatment arm and dose level for the Safety and EE populations. The corresponding two-sided 95% CI will be calculated using Clopper-Pearson [REDACTED] method. The MRD negativity rate will be presented by source of sample collection (BM, PB, BM and/or PB).

